7.0 STUDY CALENDAR

Baseline evaluations are to be conducted within 3 weeks prior to start of protocol therapy. Scans and x-rays must be done no more than 3 weeks prior to the start of ablation.

	Baseline	Ablation	1 day after ablation	1 month after ablation	Follow-up ^d	Progression
Physical exam, incl. medical history, weight, VS, PS	X					
CBC	X					
CMP	X					
PT/PTT and INR	X					
Pregnancy test ^a	X					
IR evaluation ^b	X					
CT or PET scan					X ^d	
FACT-G7	X		X	X		X
BPI short form	X		X	X		X
Adverse events		X ^c				
Survival follow-up						X ^e

a: Women of childbearing potential only

b: Patients must have 10 or fewer treatable lesions when enrolled in the study and will be seen in consultation by an experienced interventional oncologic radiologist with evaluation of available PET, CT, MR, and US images for eligibility and lesion accessibility

c: Tracked for 30 days following ablation

d: The patients will be imaged as per routine care at the following time points: 6 weeks post first-procedure, every 9 weeks for the first year, every 12 weeks for the second year, and every 6 months for 5 years or until death or radiographic progression, whichever comes first.

e. After progression, patients will be followed every 3 months for survival only.

8.0 DATA SUBMISSION SCHEDULE

Case report forms with appropriate source documentation will be completed according to the schedule listed in this section.

Case Report Form	Submission Schedule
Original Consent Form	Prior to registration
Registration Form Eligibility Form On-Study Form	Prior to starting treatment
Ablation Form	After treatment
Toxicity Form	30 days following ablation
Tumor Measurement Form Follow Up Form	Baseline 6 weeks after ablation Every 9 weeks during Year 1 Every 12 weeks during Year 2 Every 6 months for all subsequent years for 5 years or until progression or death Every 3 months after progression (survival only)
QOL Form	Baseline 1 day after ablation 1 month after ablation Progression

9.0 MEASUREMENT OF EFFECT

9.1 Antitumor Effect – Solid Tumors

There will be another PET/CT at 42 +/- 3 days following the last procedure (approximately 6 weeks post-procedure) and one every 9 weeks thereafter until progression of disease. All imaging is standard of care.

For the purposes of this study, patients should be re-evaluated for response every 9 weeks. In addition to a baseline scan, confirmatory scans should also be obtained 4 weeks (not less than 4) weeks following initial documentation of objective response.

Response and progression will be evaluated in this study using the new international criteria proposed by the revised Response Evaluation Criteria in Solid Tumors (RECIST) guideline (version 1.1) [Eur J Ca 45:228-247, 2009]. Changes in the largest diameter (unidimensional measurement) of the tumor lesions and the shortest diameter in the case of malignant lymph nodes are used in the RECIST criteria.

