Tumor Ablation in Metastatic Sarcoma Stable on Chemotherapy

**Washington University School of Medicine
Division of Oncology
[name]
[name]**

**Protocol#: 201309108
Version Date: 05/17/17**

Principal Investigator: [name] [name]., Ph.D.
[contact]
E-mail: [contact]

Sub-Investigators	Modality
[name].	Medical Oncology
[name].	Radiology
[name].	Biostatistics

Clinical Trials.gov# NCT01986829

CONFIDENTIAL

The information contained in this document is regarded as confidential and, except to the extent necessary to obtain informed consent, may not be disclosed to another party unless law or regulations require such disclosure. Persons to whom the information is disclosed must be informed that the information is confidential and may not be further disclosed by them

Tumor Ablation in Metastatic Sarcoma Stable on Chemotherapy

Protocol Revision History

Initial Approval Version	09/09/2013
Amendment #1 Version	10/06/2014
Amendment #2 Version	12/20/2016
Amendment #3 Version	05/17/2017

Tumor Ablation in Metastatic Sarcoma Stable on Chemotherapy

SCHEMA

Eligible Patients

Patients with high-grade metastatic sarcoma stable on chemotherapy for 6-12 cycles with 10 or fewer metastatic lesions which are amenable to ablation and which are measurable by CT, PET/CT, or MRI

Treatment Plan

Chemotherapy stopped at initiation of ablation therapy. All ablation therapy completed within 3 weeks with CT/PET every 9 weeks for the first year, every 12 weeks for the second year, and then every 6 months until radiographic progression or 5 years

Glossary of Abbreviations

AE	Adverse event
ALT (SGPT)	Alanine transaminase (serum glutamate pyruvic transaminase)
ANC	Absolute neutrophil count
AST (SGOT)	Aspartate transaminase (serum glutamic oxaloacetic transaminase)
BPI	Brief Pain Inventory
CBC	Complete blood count
CFR	Code of Federal Regulations
CMP	Complete metabolic panel
CR	Complete response
CRF	Case report form
CT	Computed tomography
CTCAE	Common Terminology Criteria for Adverse Events
CTEP	Cancer Therapy Evaluation Program
DOB	Date of birth
DSM	Data and Safety Monitoring
ECOG	Eastern Cooperative Oncology Group
FDA	Food and Drug Administration
HRPO	Human Research Protection Office (IRB)
INR	International normalized ratio
IR	Interventional radiology
IRB	Institutional Review Board
IULN	Institutional upper limit of normal
MRI	Magnetic resonance imaging
NCI	National Cancer Institute
NIH	National Institutes of Health

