2.0 OBJECTIVES

2.1 Primary Objectives

To determine the progression-free rate at 3 months in patients with metastatic sarcoma stable on chemotherapy whose lesions have undergone ablation. PFR is defined as the percentage of patients with no progression (local recurrence of an ablated lesion or the appearance of a new lesion) at 3 months after ablation.

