5.10 Duration of Follow-up

Patients will be followed every 9 weeks for the first year, every 12 weeks for the second year, and then every 6 months for 5 years or until death, progression, consent is withdrawn, or the study is closed, whichever occurs first. Patients will be followed by CT or PET scan and office visits every 9 weeks. CT and PET scans can be performed at outside facilities and mailed to us for review by our radiologists. Patients removed from study for unacceptable adverse events will be followed until resolution or stabilization of the adverse event. After progression, patients will be followed for survival every 3 months.

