9.4.5 Other Definitions

Progression-free rate: PFR is defined as the percentage of patients with no progression (local recurrence of an ablated lesion or the appearance of a new lesion) at 3 months after ablation.

Overall survival: OS is defined as the time from diagnosis of metastatic disease to the time of death.

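### The imaging sections disagree on anchor and timetable, and none fixes the scan that decides 3-month progression status, so the primary estimate need not measure status at 3 months.

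*Combined protocol and SAP*

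**What the plan says.** The endpoint in 2.1 is the share of patients free of progression ("local recurrence of an ablated lesion or the appearance of a new lesion) at 3 months after ablation"). Section 9.4.5 repeats it: "Progression-free rate: PFR is defined as the percentage of patients with no progression". Neither says whether the 3 months run from the first or the last procedure, although the schema lets ablation spread over up to 3 weeks.

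The imaging sections read as follows.

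- Section 9.1: "There will be another PET/CT at 42 +/- 3 days following the last procedure (approximately 6 weeks post-procedure) and one every 9 weeks thereafter". Anchor: last procedure.
- Section 7.0, footnote d: "6 weeks post first-procedure, every 9 weeks for the first year". Anchor: first procedure.
- Section 8.0, tumor measurement form: "6 weeks after ablation Every 9 weeks during Year 1". Anchor: unspecified.
- Section 5.10: "Patients will be followed by CT or PET scan and office visits every 9 weeks". No 6-week scan and no anchor.
- Schema: "All ablation therapy completed within 3 weeks with CT/PET every 9 weeks for the first year". No 6-week scan and no anchor.

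Section 9.1 adds, for responders, that "confirmatory scans should also be obtained 4 weeks (not less than 4) weeks following initial documentation of objective response". A footnote to the best-response table in 9.4.3 limits confirmation to non-randomized trials with response as the primary endpoint.

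Section 11.1 sizes the trial at 36 patients for 20% against 40% with a two-sided one-sample proportion test. Section 11.2 plans Kaplan-Meier estimates of 3-month PFS. Nothing says which of the two decides the trial.

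**The concern.** Progression here means local recurrence or a new lesion, which is mostly seen on imaging. A rate at week 13 is measured only if patients are imaged near week 13. If they are not, a Kaplan-Meier curve with progression dated when documented stays flat from the last scan to the next, and its value at day 91 is the value at the last scan. There is no explicit dating rule for PFS. The nearest rules are in 9.4.4, which ends duration of response at objective documentation, and in 9.3, which backdates only to an earlier abnormal FDG-PET.

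Anchor, timetable, deciding scan and estimator could therefore all be settled after the data are seen, and the same patients could pass or fail the 20% against 40% test on that choice. Section 5.9 adds to this. A patient judged to need chemotherapy counts as progressed but is also replaced, so it is unclear whether the event stays in the primary analysis.

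**Working it through.** **1. The plan's own figure.** Inputs from 11.1: null 0.20, alternative 0.40, two-sided 0.05, power 80%. With the normal approximation, n = ((1.960·√(0.20·0.80) + 0.842·√(0.40·0.60)) / 0.20)² = 35.8, rounded to 36; power at 36 is 80.2%. The sample size reproduces and is not in dispute. With exact binomial tails at n = 36:

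- 13 or more successes: upper tail 0.018 at 20%, power 0.738 at 40%. This is the exact two-sided cut-off (p = 0.021).
- 12 or more successes: upper tail 0.042, power 0.838. This passes the normal-approximation test (z = 2.00) but not the exact one (p = 0.058).

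**2. Where the scans fall.** Three months is taken as day 91 (week 13). For one session, first and last procedure coincide.

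| Source | Routine scan days | Last before day 91 | Next |
|---|---|---|---|
| 9.1 | 42 (39–45), 105 (102–108) | week 6 | week 15 |
| 7.0 and 8.0, 9-weekly after the 6-week scan | 42, 105 | week 6 | week 15 |
| 7.0 and 8.0, 9-weekly from ablation | 42, 63, 126 | week 9 | week 18 |
| 5.10 and schema | 63, 126 | week 9 | week 18 |

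The first two rows are the most natural reading. Day 91 lies in a gap in every row.

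**3. Exceptions.**

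- Treatment spread over 14 to 21 days, scans at 6 and 15 weeks from the first procedure, 3 months counted from the last: the second scan falls on day 105 − 14 = 91 to 105 − 21 = 84.
- Same spread, 9-weekly scans from the last procedure, 3 months counted from the first: the first scan falls on day 63 + 14 = 77 to 63 + 21 = 84.
- Responders with a confirmatory scan: week 6 + 4 = 10 or week 9 + 4 = 13 at the earliest, if the 9.4.3 footnote lets confirmation apply.

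The documents do not give the share of patients in these groups.

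**4. Possible size (illustration).** Assumptions not in the documents: 20% is the true week-13 rate; Weibull hazard with shape k; progression found only at routine scans; no dropout. Without dropout the Kaplan-Meier value at day 91 equals the simple proportion, so the binomial rule applies. The rate read at day 91 from a last scan at week t is 0.20^((t/13)^k).

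| Last scan | k | Rate read | P(13 or more of 36) | P(12 or more of 36) |
|---|---|---|---|---|
| week 6 | 0.7 | 0.392 | 0.71 | 0.81 |
| week 6 | 1.0 | 0.476 | 0.94 | 0.97 |
| week 6 | 1.5 | 0.604 | 1.00 | 1.00 |
| week 9 | 0.7 | 0.288 | 0.21 | 0.33 |
| week 9 | 1.0 | 0.328 | 0.40 | 0.54 |
| week 9 | 1.5 | 0.396 | 0.72 | 0.82 |

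The design values are 0.018 and 0.042.

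Progression found between scans lowers these. With constant hazard and half of progressions found at onset, the rate read is 0.20 + 0.5·(0.476 − 0.20) = 0.338 for week 6 and 0.20 + 0.5·(0.328 − 0.20) = 0.264 for week 9. P(13 or more) is then 0.45 and 0.13.

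**5. Dependence on the reference rates.** Suppose instead that the 20% was itself read from scans, last at week b, and the trial reads at week t. Under constant hazard and scan-only detection the trial reads 0.20^(t/b).

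| b | t | Rate read | P(13 or more of 36) |
|---|---|---|---|
| equal to t | t | 0.200 | 0.018 |
| 9 | 6 | 0.342 | 0.47 |
| 12 | 6 | 0.447 | 0.89 |
| 12 | 9 | 0.299 | 0.26 |
| 8 | 9 | 0.164 | 0.003 |

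The shift can be large, nil or reversed.

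**The case against.** Several points on the other side carry weight.

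- **The benchmark.** Section 11.1 takes its rates from a clinical trials database, so 20% is probably also a rate of documented progression. What matters then is the trial's scan timing relative to the reference timing. This stands, and it is why step 4 cannot be read as an actual false-positive rate.
- **The anchor.** The surveys in 5.5 and the toxicity window in 5.6 run from the first procedure, and stable disease in 9.4.4 runs from the start of treatment. These point towards the first procedure, and for single-session patients the conflict disappears. But none of them defines the origin for PFR, and 9.1 names the last procedure for the very scan that feeds it.
- **The timetable.** The schema and 5.10 may simply be summaries that leave out the 6-week scan, and scans at weeks 6, 9 and 18 are a strained reading. If so, the timetable is weeks 6 and 15, and week 13 is still in a gap.
- **The estimator.** The endpoint is defined as a percentage and powered on a proportion test, so Kaplan-Meier may be only descriptive. The plan does not say so, and a proportion test still needs a rule for which scan supplies the status at 3 months.

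A reader might infer that the plan raises the false-positive risk to a known level, such as 0.94, or that this is an upper bound. The documents do not support either: the value depends on the hazard shape, on progression found between scans and on the unknown reference timing. Nor do they support saying that most patients lack a scan near 3 months. The statement holds for patients treated in one session without an extra scan.

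**Conclusion.** The point holds. The sections conflict on anchor (first, last or unspecified procedure) and on whether a 6-week scan exists, and no section schedules a scan at 3 months for all patients or names the one that decides 3-month status. For single-session patients without an extra scan, a Kaplan-Meier figure at day 91, with progression dated when documented, reports status at week 6 or 9. The primary result cannot be computed in one way only from the plan as written.

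The numerical effect is not established. The ranges of 0.71 to 1.00 and 0.21 to 0.72 against 0.018 rest on scan-only detection, Weibull shapes from 0.7 to 1.5, and 20% being the true week-13 rate. They show that the choice of scan could decide the trial. Net size and direction remain unknown until the scan timing behind the reference rates is stated.

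**What to change.** 1. Reconcile the schema, 5.10, 7.0, 8.0 and 9.1 to one anchor and one timetable, chosen by the investigators, and state that anchor in 2.1 and 9.4.5.
2. Then either let that timetable place an already planned scan in a stated window around 3 months, or define the primary endpoint as status at a named scheduled scan and restate the null rate, alternative rate and power for that time.
3. Make the 11.1 proportion test on status at that scan the primary analysis, or use an interval-censored estimate, in place of the Kaplan-Meier reading at day 91.
4. State how progression found between scans is dated and counted. Reconcile 5.9 so that patients taken off and replaced after being considered progressed remain counted as progressions.
5. State what is known of the scan timing behind the 20% and 40% rates.

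The cost is protocol and SAP wording, and possibly a shift in the timing of one routine scan. Moving the endpoint to a named scan shifts no imaging, but needs planning rates that the documents do not give. No particular scan timetable is proposed here.

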9.2 Disease Parameters

Measurable disease: Measurable lesions are defined as those that can be accurately measured in at least one dimension (longest diameter to be recorded) as >20 mm by chest x-ray, as >10 mm with CT scan, or >10 mm with calipers by clinical exam. All tumor measurements must be recorded in millimeters (or decimal fractions of centimeters).

Note: Tumor lesions that are situated in a previously irradiated area might or might not be considered measurable. If the investigator thinks it appropriate to include them, the conditions under which such lesions should be considered must be defined in the protocol.

Malignant lymph nodes: To be considered pathologically enlarged and measurable, a lymph node must be >15 mm in short axis when assessed by CT scan (CT scan slice thickness recommended to be no greater than 5 mm). At baseline and in follow-up, only the short axis will be measured and followed.

Non-measurable disease: All other lesions (or sites of disease), including small lesions (longest diameter <10 mm or pathological lymph nodes with ≥ 10 to <15 mm short axis), are considered non-measurable disease. Bone lesions, leptomeningeal disease, ascites, pleural/pericardial effusions, lymphangitis cutis/pulmonitis, inflammatory breast disease, and abdominal masses (not followed by CT or MRI), are considered as non-measurable.

Note: Cystic lesions that meet the criteria for radiographically defined simple cysts should not be considered as malignant lesions (neither measurable nor non-measurable) since they are, by definition, simple cysts.

‘Cystic lesions’ thought to represent cystic metastases can be considered as measurable lesions, if they meet the definition of measurability described above. However, if non-cystic lesions are present in the same patient, these are preferred for selection as target lesions.

Target lesions: All measurable lesions up to a maximum of 2 lesions per organ and 5 lesions in total, representative of all involved organs, should be identified as target lesions and recorded and measured at baseline. Target lesions should be selected on the basis of their size (lesions with the longest diameter), be representative of all involved organs, but in addition should be those that lend themselves to reproducible repeated measurements. It may be the case that, on occasion, the largest lesion does not lend itself to reproducible measurement in which circumstance the next largest lesion which can be measured reproducibly should be selected. A sum of the diameters (longest for non-nodal lesions, short axis for nodal lesions) for all target lesions will be calculated and reported as the baseline sum diameters. If lymph nodes are to be included in the sum, then only the short axis is added into the sum. The baseline sum diameters will be used as reference to further characterize any objective tumor regression in the measurable dimension of the disease.

Non-target lesions: All other lesions (or sites of disease) including any measurable lesions over and above the 5 target lesions should be identified as non-target lesions and should also be recorded at baseline. Measurements of these lesions are not required, but the presence, absence, or in rare cases unequivocal progression of each should be noted throughout follow-up.

9.3 Methods for Evaluation of Measurable Disease

All measurements should be taken and recorded in metric notation using a ruler or calipers. All baseline evaluations should be performed as closely as possible to the beginning of treatment and never more than 4 weeks before the beginning of the treatment.

The same method of assessment and the same technique should be used to characterize each identified and reported lesion at baseline and during follow-up. Imaging-based evaluation is preferred to evaluation by clinical examination unless the lesion(s) being followed cannot be imaged but are assessable by clinical exam.

Clinical lesions: Clinical lesions will only be considered measurable when they are superficial (e.g., skin nodules and palpable lymph nodes) and ≥ 10 mm diameter as assessed using calipers (e.g., skin nodules). In the case of skin lesions, documentation by color photography, including a ruler to estimate the size of the lesion, is recommended.

Chest x-ray: Lesions on chest x-ray are acceptable as measurable lesions when they are clearly defined and surrounded by aerated lung. However, CT is preferable.

Conventional CT and MRI: This guideline has defined measurability of lesions on CT scan based on the assumption that CT slice thickness is 5 mm or less. If CT scans have slice thickness greater than 5 mm, the minimum size for a measurable lesion should be twice the slice thickness. MRI is also acceptable in certain situations (e.g. for body scans).

Use of MRI remains a complex issue. MRI has excellent contrast, spatial, and temporal resolution; however, there are many image acquisition variables involved in MRI, which greatly impact image quality, lesion conspicuity, and measurement. Furthermore, the availability of MRI is variable globally. As with CT, if an MRI is performed, the technical specifications of the scanning sequences used should be optimized for the evaluation of the type and site of disease. Furthermore, as with CT, the modality used at follow-up should be the same as was used at baseline and the lesions should be measured/assessed on the same pulse sequence. It is beyond the scope of the RECIST guidelines to prescribe specific MRI pulse sequence parameters for all scanners, body parts, and diseases. Ideally, the same type of scanner should be used and the image acquisition protocol should be followed as closely as possible to prior scans. Body scans should be performed with breath-hold scanning techniques, if possible.

PET-CT: At present, the low dose or attenuation correction CT portion of a combined PET-CT is not always of optimal diagnostic CT quality for use with RECIST measurements. However, if the site can document that the CT performed as part of a PET-CT is of identical diagnostic quality to a diagnostic CT (with IV and oral contrast), then the CT portion of the PET-CT can be used for RECIST measurements and can be used interchangeably with conventional CT in accurately measuring cancer lesions over time. Note, however, that the PET portion of the CT introduces additional data which may bias an investigator if it is not routinely or serially performed.

Ultrasound: Ultrasound is not useful in assessment of lesion size and should not be used as a method of measurement. Ultrasound examinations cannot be reproduced in their entirety for independent review at a later date and, because they are operator dependent, it cannot be guaranteed that the same technique and measurements will be taken from one assessment to the next. If new lesions are identified by ultrasound in the course of the study, confirmation by CT or MRI is advised. If there is concern about radiation exposure at CT, MRI may be used instead of CT in selected instances.

Endoscopy, Laparoscopy: The utilization of these techniques for objective tumor evaluation is not advised. However, such techniques may be useful to confirm complete pathological response when biopsies are obtained or to determine relapse in trials where recurrence following complete response (CR) or surgical resection is an endpoint.

Tumor markers: Tumor markers alone cannot be used to assess response. If markers are initially above the upper normal limit, they must normalize for a patient to be considered in complete clinical response

Cytology, Histology: These techniques can be used to differentiate between partial responses (PR) and complete responses (CR) in rare cases (e.g., residual lesions in tumor types, such as germ cell tumors, where known residual benign tumors can remain).

The cytological confirmation of the neoplastic origin of any effusion that appears or worsens during treatment when the measurable tumor has met criteria for response or stable disease is mandatory to differentiate between response or stable disease (an effusion may be a side effect of the treatment) and progressive disease.

FDG-PET: While FDG-PET response assessments need additional study, it is sometimes reasonable to incorporate the use of FDG-PET scanning to complement CT scanning in assessment of progression (particularly possible 'new' disease). New lesions on the basis of FDG-PET imaging can be identified according to the following algorithm:

- Negative FDG-PET at baseline, with a positive FDG-PET at follow-up is a sign of PD based on a new lesion.
- No FDG-PET at baseline and a positive FDG-PET at follow-up: If the positive FDG-PET at follow-up corresponds to a new site of disease confirmed by CT, this is PD. If the positive FDG-PET at follow-up is not confirmed as a new site of disease on CT, additional follow-up CT scans are needed to determine if there is

truly progression occurring at that site (if so, the date of PD will be the date of the initial abnormal FDG-PET scan). If the positive FDG-PET at follow-up corresponds to a pre-existing site of disease on CT that is not progressing on the basis of the anatomic images, this is not PD.

- FDG-PET may be used to upgrade a response to a CR in a manner similar to a biopsy in cases where a residual radiographic abnormality is thought to represent fibrosis or scarring. The use of FDG-PET in this circumstance should be prospectively described in the protocol and supported by disease-specific medical literature for the indication. However, it must be acknowledged that both approaches may lead to false positive CR due to limitations of FDG-PET and biopsy resolution/sensitivity.

Note: A 'positive' FDG-PET scan lesion means one which is FDG avid with an uptake greater than twice that of the surrounding tissue on the attenuation corrected image.

